7.3. Discontinuation from Trial Procedures

Patients can decline to continue receiving IP and/or other protocol-required therapies or procedures at any time during the trial but continue participation in the trial. If this occurs, the investigator is to discuss with the patient the appropriate processes for discontinuation from IP or other protocol-required therapies and must discuss with the patient the options for continuation of the SoA (Section 1.3) including different options of follow-up (eg, in person, by phone/mail, through family/friends, in correspondence/communication with other treatment physicians, from the review of medical records) and collection of data, including endpoints and AEs. Patients who have discontinued IP and/or protocol required therapies or procedures should not be automatically removed from the trial. Whenever safe and feasible it is imperative that patients remain on-trial to ensure safety surveillance and/or collection of outcome data. The investigator must document the change to the SoA (Section 1.3) and the level of follow-up that is agreed to by the patient (eg, in person, by telephone/mail, through family/friends, in correspondence/communication with other physicians, from review of the medical records).

7.4. Patient Consent Withdrawal

Patients have the right to withdraw consent and no longer participate in the trial at any time and for any reason without prejudice to their future medical care by the physician or at the institution. Consent withdrawal means the patient no longer wishes to undergo any follow-up visits, trial procedures, investigator contact, and non-patient contact follow-up (eg, medical records check).

- Discontinuing IP should be distinguished from consent withdrawal for follow-up since the patient may agree to undergo trial procedures or still be contacted even though they have stopped taking IP (see [Section 7.3](#)).
- Consent withdrawal should be accompanied by documentation of the reason for withdrawal. Patients requesting consent withdrawal for any follow-up should be informed that it may limit the public health value of the trial.

Patients who withdraw consent should be asked explicitly about the contribution of possible AEs to their decision to withdraw consent, and any AE information elicited should be documented.

Preferably, the patient should withdraw consent in writing and, if the patient or the patient's representative refuses or is physically unable, the site should document and sign the reason for the patient's failure to withdraw consent in writing. The ICF for the trial may note that although a patient is completely free to leave the trial and stop taking IP, the investigators hope the patient will remain for follow-up status evaluations.

For patients who have withdrawn consent for further follow-up, investigators may review public records as permitted by applicable law to determine vital status of the patient before or at the end of the trial.

7.5. Lost to Follow up

A patient will be considered lost to follow-up if he or she repeatedly fails to return for scheduled visits and is unable to be contacted by the site.

The following actions must be taken if a patient fails to return to the clinic for a required trial visit:

- The site must attempt to contact the patient or the patient's family and reschedule the missed visit as soon as possible and counsel the patient on the importance of maintaining the assigned visit schedule and ascertain whether the patient wishes to and/or should continue in the trial.
- Before a patient is deemed lost to follow up, the investigator or designee must make every effort to regain contact with the patient or the patient's family (where possible, 3 telephone calls and, if necessary, a certified letter to the patient's last known mailing address or local equivalent methods). These contact attempts should be documented in the patient's medical record.
- Should the patient continue to be unreachable, he/she will be considered to have discontinued from the trial and is lost to follow-up.

Closing of specific sites or discontinuation of the trial are handled as part of Appendix 1 ([Section 10.1.8](#)).

8. TRIAL ASSESSMENTS AND PROCEDURES

Trial assessments and procedures and their timing are summarized in the SoA ([Section 1.3](#)). Protocol waivers or exceptions are not allowed. Adherence to the trial design requirements, including those specified in the SoA, is essential and required for trial conduct.

There will be a total of 11 in-person trial visits per patient, with windows to aid in scheduling as shown in [Table 5](#). If a patient visit must be scheduled outside the visit window, the Medical Monitor should be contacted.

Table 5: CY 6031 Visit Windows

Visit	Visit Window
Screening	Up to 42 days prior to Day 1 visit
Day 1 (First Dosing Day)	N/A
Week 2	+3 days
Week 4	+3 days
Week 6	+3 days
Week 8	+3 days
Week 12	±3 days
Week 16	±7 days
Week 20	±7 days
Week 24 (EOT)	±7 days
Week 28 (EOS)	+7 days

All visits should be scheduled based on Day 1

8.1. Visit Schedule

Activities will be completed during clinic visits as described in this section. General guidance for the preferred order of assessments and procedures are outlined below:

- On visit days, patients should wait to take their daily IP dose at the clinic.
- Patient-reported outcomes questionnaires should be completed by patients prior to any other activities. (ie, KCCQ (administered first), EQ-5D-5L, SAQ-7, Patient Global Impression of Change [PGI-C])
- IP should be administered after completion of vital signs, ECG, and blood draws.
- ECGs and vital signs must be performed prior to blood draws or other invasive procedures.
- Echocardiograms should be done prior to IP dosing on Day 1 and 2 hours after IP dosing in the clinic at other time points.
- CPET should be performed after other visit activities including IP administration. CMR should occur after CPET if the assessments are performed on the same day.

Please refer to the study manuals for additional details.

8.1.1. Screening Visit

All screening evaluations must be completed and reviewed to confirm that potential patients meet all eligibility criteria. The investigator will maintain a screening log to record details of all patients screened and to confirm eligibility or record reasons for screening failure, as applicable.

Laboratory values obtained at screening and reported through the central laboratory will be used to determine patient eligibility.

The screening period will be up to 6 weeks in duration to allow greater flexibility for visit scheduling and the potential for retesting.

The CPET should not be completed until the patient is otherwise deemed eligible. The CPET used for eligibility should be completed within four weeks but not less than one week prior to randomization.

8.1.2. Day 1

Patients who meet all eligibility criteria including confirmation from the CPET core laboratory at the end of the screening period will return to the site for randomization and Day 1 activities as defined in the SoA.

8.1.3. Weeks 2 through 20

Please refer to the SoA ([Section 1.3](#)) for Weeks 2-20.

8.1.4. Week 24: End of Treatment Visit

Week 24 is defined as the EOT visit and includes assessments and procedures critical for analysis of the trial's endpoints. These assessments are outlined in the Schedule of Activities. Additionally, the following should be considered in advance of Week 24:

- Contact patients shortly before the Week 24 EOT visit to confirm their ability to perform the CPET, and schedule the procedure to ensure it is completed within the protocol-defined window
- For patients temporarily unable to exercise on the treadmill or bicycle (whichever modality was used at baseline) due to an adverse event (eg, ankle sprain, upper respiratory infection, migraine), but not due to HCM symptoms, or if the site is unable to perform the CPET (eg, equipment malfunction), then the Week 24 visit may be postponed by up to 4 weeks and those patients should continue to receive IP until the visit
- Schedule CMR imaging for sub-study (if applicable)
 - For patients who provided consent and completed baseline imaging at screening, schedule the CMR imaging to ensure it is completed within the protocol-defined window. The baseline CMR should be performed within the 6-week screening period prior to randomization.

- The EOT CMR should be performed after the Week 20 visit, but prior to the last dose of IP at Week 24.
- If necessary, the Week 24 visit may be split across two consecutive days within the visit window. If the visit is split, all assessments, except the CPET, should occur on the first day of the split visit. The CPET should occur on the second day of the split visit. Dosing will occur on site on both split visit days.

8.1.5. Week 28: End of Study Visit

All patients should complete an end of study (EOS) visit:

- For subjects who complete all study visits, the EOS visit will occur at Week 28 (or 4 weeks after a delayed Week 24 visit).
- For subjects who early-terminate IP more than 4 weeks before Week 24 and continue to stay on-study for all follow-up assessments, the Week 24 visit can be considered the EOS visit (and the EOS visit does not need to be performed).
- For subjects who withdraw consent and do not wish to continue the participation in follow-up assessments, an EOS visit should be performed 4 weeks after their final IP dose if possible.

To ensure a 4-week safety follow-up (to assess any Adverse Events), the EOS Exit Date must correspond to either 4 weeks after last dose, or at their last study visit (ie, Week 24), whichever is later.

Screening assessments for entry into an open-label extension study of aficamten are permitted at the EOS visit. CY 6031 EOS visit assessments must occur before the open-label screening assessments. Assessments for each visit must be done in the order defined by the protocol.

8.1.6. Early Discontinuation Visit

For patients who discontinue the trial prematurely, the activities outlined in the SoA will be completed during an Early Discontinuation visit as soon as possible.

8.1.7. Unscheduled Visit

Assessments may be completed at the investigator's discretion during an Unscheduled visit. In addition, assessments performed at a scheduled visit that are not defined in the SOA will be considered unscheduled assessments.

8.2. Efficacy Assessments

8.2.1. Cardiopulmonary Exercise Testing

All patients will undergo CPET with gas-exchange analysis and the methodology will be standardized across all participating sites, as described in the CPET manual. Testing will include continuous ECG monitoring by trained personnel and be performed in an area that is equipped for cardiopulmonary resuscitation. Treadmill is the preferred modality for exercise testing. For CPET laboratories that do not perform treadmill testing, cycle ergometry is an acceptable alternative. Exercise protocols for both modalities will be provided in the CPET manual. Patients

must use the same testing modality for all exercise tests during the trial. Whenever possible, CPET should be administered by the same trial personnel using the same equipment and performed after the other trial procedures on that visit day (including echocardiogram, KCCQ, EQ-5D-5L, CGI, PGI-C, NYHA class, SAQ-7, vital signs, ECG, blood sampling, IP administration). Patients naïve to exercise protocols will be familiarized with the technique during screening.

All CPET testing will be symptom-limited and patients will be strongly encouraged to achieve maximal exertion and an RER ≥ 1.05 . The reason(s) for termination of sub-maximal exercise tests will be documented. A test will be identified as being maximal effort if the RER is ≥ 1.05 .

Patients should not engage in strenuous exercise for 24 hours prior to the CPET, and patients should not exercise at all within 12 hours prior to the test. Patients should fast for at least 4 hours prior to CPET. All regularly scheduled medications should be taken as normal. Patients should avoid taking medications that cause drowsiness within 8 hours prior to the test. Weight should be collected immediately prior to each CPET.

The Week 24 CPET should be performed at approximately the same time of day (eg, morning, mid-day, afternoon) as the baseline CPET at screening, at a consistent time after the last dose of beta-blocker and IP. Whenever possible, patients should perform exercise testing between three and ten hours after taking beta blocking agents.

If a life-threatening arrhythmia, early ischemia, severe hypotension or other serious finding is identified by the investigator during CPET, the patient will be asked to stop the exercise test, and his/her physicians will be notified of the results. If the patient is performing the screening test, s/he will not be randomized to the trial. Enrolled patients who have a non-life-threatening event or finding that stops the test can resume testing when it is safe to do so and after appropriate treatment, per the investigator.

All sites must be qualified by the CPET core laboratory prior to the initiation of screening. To qualify, sites will perform an exercise test on two healthy adults and submit them for core laboratory review. Sites may be required to submit additional normal exercise tests during the conduct of the trial for review by the CPET core laboratory in order to confirm proper function of testing equipment. Sites may be qualified based on exercise tests recently reviewed by the CPET core laboratory during the conduct of other trials.

8.2.2. Echocardiography

Echocardiography will be done during screening and prior to dosing on Day 1.

Echocardiography will be performed 2 hours (± 30 min) after dosing in the clinic on Weeks 2, 4, 6, 8, 12, 16, 20, and 24. Echocardiography will also be performed at Week 28.

Certified sonographers will perform echocardiography using standard high-quality, high-fidelity machines approved by Cytokinetics. Whenever possible, the same sonographer will perform all studies for a single patient. Echocardiograms will be performed after the patient has been resting in a supine position for at least 10 minutes and in accordance with the echocardiography manual. Instructions for the performance of the Valsalva maneuver and imaging the LVOT-G will also be included in the echocardiography manual.

When echocardiograms are scheduled at the same time as blood draws, vital signs, and/or ECGs, the order of evaluation will be vital signs, ECGs, blood draw and echocardiogram. The blood draw should be obtained at the scheduled time point and the echocardiograms will follow.

Echocardiographic parameters to be measured will at least include the left ventricular parameters in [Table 6](#) in addition to right heart function metrics detailed in the echocardiography protocol.

Table 6: CY 6031 Echocardiographic LV Parameters to be Measured

Resting LVOT-G	LVEDV	IVST
Post-Valsalva LVOT-G	LVESD	IVCT
LVEF	LVESV	IVRT
LVFS	LVCO	E/E' ratio (septal and lateral)
GLS	LV Stroke Volume	LAV
LVEDD	LVOT VTI	

GLS = global longitudinal strain; IVCT = isovolumic contraction time; IVRT = isovolumic relaxation time; IVST = interventricular septum thickness; LAV = left atrial volume; LVCO = left ventricular cardiac output; LVEDD = left ventricular end diastolic diameter; LVEDV = left ventricular end diastolic volume; LVESD = left ventricular end systolic diameter; LVESV = left ventricular end systolic volume; VTI = velocity time integral.

Unscheduled echocardiograms may be obtained when clinically indicated, for example to assess an AE or follow-up a clinically significant change in a prior echocardiogram, as determined by the investigator. Results will be interpreted by the unmasked echocardiologist at the investigational site.

All echocardiograms (including unscheduled) will be sent to the core laboratory for interpretation. On-site interpretation of LVEF and LVOT-G will be used for dose escalation and reduction decisions via IWRS. The core laboratory quantification of the echocardiograms will be used for all statistical analyses.

8.2.3. Cardiac Magnetic Resonance

A CMR imaging sub-study will assess the effects of administration of CK-3773274 dosing on cardiac morphology, function, and fibrosis in approximately 100 oHCM patients who are eligible and consent to participate. CMR will be performed during screening period and Week 24. CMR should occur after CPET if the assessments are performed on the same day.

Patients with eGFR <30 mL/min/1.73 m² or an allergy to gadolinium may have a non-contrast CMR.

Patients who screen fail and rescreen do not need a repeat CMR.

8.2.4. New York Heart Association Functional Classification

After interviewing the patient, the investigator (or qualified designee) will record the NYHA Functional Classification in the CRF ([Criteria Committee of the New York Heart 1994](#)). The NYHA classification is as follows:

- Class I - No symptoms and no limitation in ordinary physical activity (eg, shortness of breath when walking, climbing stairs)

- Class II - Mild symptoms (eg, mild shortness of breath and/or angina) and slight limitation during ordinary activity.
- Class III - Marked limitation in activity due to symptoms, even during less-than-ordinary activity (eg, walking short distances [20-100 m]). Comfortable only at rest.
- Class IV - Severe limitations. Experiences symptoms even while at rest. Mostly bedbound patients.

8.2.5. Clinical Global Impression Scale

The investigator (or qualified designee) will record the CGI scale assessment of the patient's global functioning in the CRF at the time points outlined in the SoA.

8.2.6. Patient-Reported Outcomes

The following questionnaires will be completed at trial visits specified in the SoA ([Section 1.3](#)):

- KCCQ
- EQ-5D-5L
- PGI-C
- SAQ-7

Patients will be asked to complete the KCCQ, EQ-5D-5L, SAQ-7 and PGI-C questionnaires in a quiet place prior to the medical consultation and prior to undergoing any tests and procedures to avoid biasing their responses.

Site staff will verify the questionnaires for completeness before the patients leave the clinic or hospital.

8.3. Safety Assessments

Planned time points for all safety assessments are provided in the SoA ([Section 1.3](#)).

8.3.1. Physical Examinations

A complete physical examination will include, at a minimum, assessments of the cardiovascular, respiratory, and neurological systems. Breast, genital, and rectal examinations are not required unless specific evaluation is warranted.

Investigators should pay special attention to clinical signs related to previous serious illnesses.

Physical examinations may be conducted at any time during the treatment period if clinically indicated.

8.3.2. Height and Weight

Height and weight will be measured while patient is fully clothed with shoes removed. Height will be measured at screening only.

8.3.3. Vital Signs

At the Screening visit, a room air oxygen saturation will be assessed.

At all visits, heart rate, respiratory rate, and blood pressure will be assessed.

Blood pressure and heart rate measurements will be assessed with the patient in a supine or sitting position. Blood pressure and heart rate measurements should be performed with an automated oscillometer after the patient has rested for at least 5 minutes in a quiet setting without distractions (eg, television, cell phones). The position selected for a patient should be the same that is used throughout the trial.

Vital signs (to be taken before blood collection for laboratory tests) will consist of 1 heart rate reading and 3 consecutive blood pressure readings recorded at intervals of at least 1 minute. The average of the 3 blood pressure readings will be recorded in the CRF.

8.3.4. Electrocardiograms

Triplicate 12-lead ECGs will be obtained as outlined in the SoA ([Section 1.3](#)) using an ECG machine that automatically calculates the heart rate and measures PR, QRS, QT, and QTc intervals.

At each time point at which triplicate ECGs are performed, three individual ECG tracings should be obtained as closely as possible in succession, but no more than 2 minutes apart.

Patients should be sitting or supine in a rested and calm state for at least 5 minutes prior to the ECG. The investigator may perform additional ECG recordings as needed for the care of the patient.

A patient will be withdrawn from the trial by the investigator or designee if, in their medical judgment, ECG findings are present which make continued trial participation not in the patient's best interest.

For safety monitoring purposes, the investigator or designee must review, sign, and date all ECG tracings.

Unscheduled ECGs may be collected at additional time points, for example in case of an AE or based on vital signs, PK results or PD results, as determined by the investigator or the Medical Monitor.

All ECG tracings will be kept as part of the patient's permanent trial file at the site. Digital recordings will be analyzed and stored at a central ECG laboratory.

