4. TRIAL DESIGN

4.1. Overall Design

This is a Phase 3, randomized, placebo-controlled, double-blind, multi-center trial in patients with symptomatic oHCM. Approximately 270 eligible patients will be randomized in a 1:1 ratio to receive CK-3773274 or placebo. Randomization will be stratified by use of beta-blockers (yes or no) and CPET exercise modality (treadmill or bicycle) and implemented in the Interactive Web Response System (IWRS). A cap on the number of patients taking beta-blockers and will not exceed approximately 70% of total enrollment. The number of patients taking disopyramide will be capped at approximately 10% of total enrollment. The number of patients with persistent atrial fibrillation at screening will also be capped at approximately 15%, and the number of patients using the bicycle CPET exercise modality will be capped at approximately 50% as well.

IP will be administered orally once daily with or without food. During the initial six weeks of the treatment period, IP doses will be individually titrated at Weeks 2, 4, and 6 using echocardiography. Dose escalation at Weeks 2, 4, and 6 will occur only if a patient has a post-Valsalva LVOT-G ≥ 30 mmHg and a biplane LVEF $\geq 55\%$. Echocardiograms will be performed at each subsequent visit during the trial and the dose down titrated if necessary. The primary endpoint of pVO₂ will be measured by CPET at screening and at end of treatment (Week 24). Patients' background HCM therapy should be individually optimized according to the local practice.

All patients will be followed according to the Schedule of Activities (SoA) from randomization through the date of their final visit irrespective of whether the patient is continuing to receive IP, unless the patient has discontinued prematurely from the trial or withdrawn consent. An early discontinuation visit will be performed for patients who discontinue prematurely from the trial.

The overall study design is described by a trial schema in [Figure 2](#).

The trial endpoints and objectives are defined in [Table 2](#).

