6.6.3. LVEF Safety Threshold

If the unmasked echocardiologist observes that the LVEF has crossed the defined safety threshold of $< 40\%$ or feels the patient requires urgent medical attention, the unmasked

echocardiologist will enter the LVEF value in the IWRS and discuss the results with the blinded investigator or qualified designee. The Medical Monitor will be informed in these cases.

If a patient's LVEF is <40% at any time, the following steps should occur after consultation with the Medical Monitor:

- IP should be stopped and held for at least 7 days.
- Repeat echocardiograms should be performed per investigator judgment until a normal LVEF ($\geq 55\%$) has been documented at which point the patient can be re-started on IP after being down-titrated.
- Document dose interruption in the eCRF and include the reason for interruption, the date of the last dose, and the restart date ([Section 7.1](#)).

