7.1. Temporary IP Interruption

Initially, any IP interruption should be considered temporary unless permanent IP discontinuation is mandated by the protocol.

A temporary IP interruption:

- Will be implemented when a predefined safety threshold has been met ([Section 6.6](#))
- May be considered by the investigator in the case of an AE/SAE or for another reason

If a temporary IP interruption occurred because a safety threshold was met, blinded treatment will be resumed at least 7 days later, either at a lower dose or with a permanent switch to placebo if the patient was at 5mg, as determined by the IWRS ([Section 6.6.3](#)).

If the IP was temporarily interrupted because of an AE/SAE, the investigator should make the best effort to resume IP as soon as practically possible, assuming there are no remaining safety concerns.

If dosing is interrupted for more than 3 consecutive days in the first 6 weeks and more than 7 consecutive days thereafter, the investigator should contact the Medical Monitor to discuss the patient.

All temporary IP interruptions of greater than 3 days should be recorded in the eCRF (stop and start dates and reason for interruption) and the Medical Monitor should be notified.

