8.4.1.10. Pregnancy and Breastfeeding

If a woman becomes pregnant while on IP, IP must be discontinued. The investigator must counsel the patient and discuss the risks of continuing with the pregnancy and the possible effects on the fetus.

Please refer to Appendix 3 ([Section 10.3](#)) regarding contraceptive guidance.

Irrespective of the treatment received by the patient, any pregnancy occurring in a female patient, or female partner of a male patient, after starting the IP up to 4 weeks following IP discontinuation must be reported to Cytokinetics within 24 hours of the investigator's knowledge of the event.

Pregnancies must be recorded in the eCRF and reported on the Cytokinetics Pregnancy form, which is emailed or faxed to Cytokinetics Drug Safety (contact details are provided on the Pregnancy Report form):

Email: [contact]

[contact]

Details of all pregnancies in female patients and female partners of male patients will be collected after the start of IP and until the conclusion of the pregnancy. The follow-up of an infant (if applicable) will be conducted up to 12 months after the birth of the child.

Any pregnancy complication or elective termination of a pregnancy for medical reasons must be reported as an AE or SAE.

Abnormal pregnancy outcomes (eg, spontaneous abortion, fetal death, stillbirth, congenital anomalies, ectopic pregnancy) are considered SAEs.

Any post-trial pregnancy-related SAE considered reasonably related to the IP by the investigator will be reported to Cytokinetics as described in [Section 8](#). While the investigator is not obligated to actively seek this information in former trial patients, he or she may learn of an SAE through spontaneous reporting.

Male Patients with Partners Who Become Pregnant

If the partner of a male subject becomes pregnant while on study drug, he may continue receiving treatment; however, he must use barrier method (ie, condom) during sexual intercourse to avoid further fetal exposure.

The investigator will attempt to collect pregnancy information on any male patient's female partner who becomes pregnant while the male patient is in this trial.

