10.5. Appendix 5: Liver Safety: Actions and Follow-up Assessments

Drug-induced Liver Injury Reporting & Additional Assessments

To facilitate appropriate monitoring for signals of DILI, cases of concurrent aspartate aminotransferase (AST) or alanine aminotransferase (ALT) and total bilirubin (TBL) and/or international normalized ratio (INR) elevation require the following:

- The event is to be reported to Cytokinetics as an SAE within 24 hours of discovery or notification of the event (ie, before additional etiologic investigations have been concluded)
- The AE CRF that captures information necessary to facilitate the evaluation of treatment-emergent liver abnormalities is to be completed and sent to Cytokinetics.

Other events of hepatotoxicity and potential DILI are to be reported as SAEs if they meet the criteria for an SAE defined in [Section 8.4.1.2](#).

Criteria for Permanent Discontinuation of Investigational Product and Other Protocol-required Therapies due to Potential Hepatotoxicity

CK-3773274 **must** be discontinued permanently and the patient should be followed according to the following recommendations for possible DILI, if ALL of the criteria below are met:

- TBL $>2 \times$ ULN or INR >1.5

AND

- increased AST or ALT from the relevant baseline value as specified below:

Baseline AST or ALT Value	AST or ALT Elevation
<ULN	$>3 \times$ ULN

AND

- no other cause for the combination of the above laboratory abnormalities is apparent; important alternative causes for elevated AST/ALT and TBL values include, but are not limited to:
 - hepatobiliary tract disease
 - viral hepatitis (eg, Hepatitis A/B/C/D/E, Epstein-Barr Virus, cytomegalovirus, Herpes Simplex Virus, Varicella, toxoplasmosis, and Parvovirus)
 - right sided heart failure, hypotension, or any cause of hypoxia to the liver causing ischemia
 - exposure to hepatotoxic agents/drugs or hepatotoxins, including herbal and dietary supplements, plants and mushrooms
 - heritable disorders causing impaired glucuronidation (eg, Gilbert's Syndrome, Crigler-Najjar syndrome) and drugs that inhibit bilirubin glucuronidation (eg, indinavir, atazanavir)

- alpha-one antitrypsin deficiency
- alcoholic hepatitis
- autoimmune hepatitis
- Wilson’s disease and hemochromatosis
- nonalcoholic fatty liver disease including steatohepatitis
- nonhepatic causes (eg, rhabdomyolysis, hemolysis)

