6.3. Protocol Deviations

Major protocol deviations are reviewed and confirmed by the protocol deviation classification committee (PDCC) during the protocol deviation reviews throughout the study prior to database lock. Major protocol deviations are a subset of protocol deviations that may significantly impact the completeness, accuracy, and/or reliability of the study data or that may significantly affect a subject's rights, safety, or well-being. E.g., of major protocol deviations are

- patients who entered the study even though they did not satisfy the entry criteria.
- patients who developed withdrawal criteria during the study but were not withdrawn.
- patients who received the wrong treatment or incorrect dose.
- patients who received an excluded concomitant treatment.

Number of patients with reported major protocol deviation will be summarized by treatment group for all randomized subjects. A summary of protocol deviations due to COVID-19 will be provided separately.

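### Protocol 8.3.4 sends an ECG safety judgment straight to withdrawal from the trial, without the Section 7 step of stopping IP or a procedure and keeping follow-up; the effect is probably very small

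*Protocol*

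**What the plan says.** Protocol 8.3.4 (Electrocardiograms) states: "A patient will be withdrawn from the trial by the investigator or designee if, in their medical judgment, ECG findings are present". The condition concerns trial participation, not dosing: "ECG findings are present which make continued trial participation not in the" patient's best interest. The paragraph does not mention Section 7.

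The opening of Protocol Section 7 names three kinds of discontinuation: a temporary IP interruption, a permanent IP stop, and withdrawal of consent by the patient. It asks that emergent safety concerns go at once to the Medical Monitor to settle whether IP continues, is interrupted or stops. Section 7.1 makes interruption the first step: "Initially, any IP interruption should be considered temporary unless permanent IP discontinuation is mandated by the protocol". Section 7.2 lists the investigator's view that further IP would harm the patient as a reason to stop IP. Section 7.2.1 encourages the patient to stay for outcome and safety data. Section 7.3 treats staying on-trial as essential where safe and feasible, and allows contact by phone, through other physicians or from records.

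Protocol 4.1 follows patients "irrespective of whether the patient is continuing to receive IP, unless the patient has discontinued prematurely from the trial or withdrawn consent". SAP 6.3 gives as one example of a major deviation "patients who developed withdrawal criteria during the study but were not withdrawn".

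**The concern.** The primary estimand (SAP 7.7.1, Table 5) uses Week 24 pVO2 from patients who stop treatment but remain in the study. A patient withdrawn under 8.3.4 falls into the exception in Protocol 4.1, so scheduled follow-up ends. The Early Discontinuation visit has no CPET in the Schedule of Activities, so Week 24 pVO2 is imputed even if the patient could have exercised.

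Other endpoints are affected too. Under SAP 7.8.1, a patient with no Week 20 or Week 24 NYHA class counts as not improved at Week 24. For a patient who was SRT eligible at baseline, status that cannot be determined after leaving is set to eligible. Safety observation is shortened as well.

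The patients at issue are those for whom IP or a maximal exercise test is unwise but a visit or a phone call is not.

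**Working it through.** **1. The rules side by side.**

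| Protocol section | Safety finding | Action |
|---|---|---|
| 8.3.4 | ECG findings, by medical judgment | Withdrawal from the trial |
| 6.6.3 | LVEF below 40% | "IP should be stopped and held for at least 7 days" |
| 8.4.1.10 | Pregnancy | "If a woman becomes pregnant while on IP, IP must be discontinued" |
| 10.5 | All liver-injury criteria met | IP must "be discontinued permanently and the patient should be followed according to the following recommendations for possible DILI" |
| 7.2, 7.2.1 | Investigator judges IP harmful | Stop IP; encourage the patient to stay |
| 8.2.1 | Serious finding during CPET | Stop the test; only a patient at screening is barred from the trial |

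Of these rules, only 8.3.4 orders a randomized patient out of the trial. Leaving the trial is a recognised status (4.1, 4.1.3, 7.5, 8.1.6). What 8.3.4 lacks is an intermediate step and a link to Section 7.

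**2. Where the texts agree and where they part.** If every form of participation is unsafe, 8.3.4 and 7.3 lead to the same place, because 7.3 is limited to what is safe and feasible. If only IP or CPET is unsafe, Section 7 stops that element and keeps the rest, while 8.3.4 offers only withdrawal.

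**3. The plan's own figure.** Inputs from Protocol 9.2: difference 1.5, SD 3.5, 135 per arm, 10% missing, two-sided 0.05.
- Evaluable per arm: 135 × 0.9 = 121.5.
- SE = 3.5 × √(2/121.5) = 0.449.
- Power: 91.4% by noncentral t, 91.6% by normal approximation. The stated figure of more than 90% reproduces.
- Three further lost values beyond the planned 27 (120 per arm) give 91.1% by t. Thirteen further (115 per arm) give 89.9%.

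**4. Possible shift in the pVO2 difference.** No ECG withdrawal rate is given, so the count k of aficamten patients withdrawn who could have exercised is assumed. So are imputation at the full 1.5 under MAR and a true off-drug effect between 0 and 0.75. The full 1.5 is taken as an upper value, since the imputation model also uses the last post-randomization NYHA class and gradients.

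Overstatement = (k/135) × (1.5 − off-drug effect)

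| Case | Off-drug effect 0 | Off-drug effect 0.75 |
|---|---|---|
| 1% of the arm | 0.01 × 1.5 = 0.015 | 0.01 × 0.75 = 0.0075 |
| k = 1 | 0.011 | 0.006 |
| k = 3 | 0.033 | 0.017 |
| k = 3, half able to exercise | 0.017 | 0.008 |

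Relative to the SE, k = 3 gives 0.0333/0.449 = 7.4% and 0.0167/0.449 = 3.7%.

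**5. If the primary imputation switches.** SAP 7.7.2 moves the primary analysis to placebo-based imputation at 10% missing (27 of 270) or 5% missing for IP-related reasons (13.5, so 14 patients). A few ECG withdrawals alone would not reach the second trigger. After a switch the imputed effect is 0 and the direction reverses: understatement of 0 to 0.01 × 0.75 = 0.0075 per 1% of the arm.

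**6. NYHA.** The Week 20 window opens on Day 127 (SAP 11.4, Table 8). If the Early Discontinuation visit is earlier and no later class falls in the Week 20 or Week 24 window, the patient counts as not improved. Each patient who would have improved moves that arm by 1/135 = 0.74 percentage points.

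**The case against.** The strongest reply is that the triggers differ. Section 8.3.4 acts only when the investigator judges trial participation itself to be against the patient's interest. An investigator who thinks only IP should stop has not made that judgment, so Section 7 governs, starting with the call to the Medical Monitor. This largely stands. A reader might infer that 8.3.4 forces out any patient with an abnormal ECG; the text does not say so, because withdrawal rests on individual medical judgment. What survives is narrower: 8.3.4 frames an ECG concern only as a question of participation and never points to the alternative.

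A reader might also infer from SAP 6.3 that a site that stopped IP and kept following the patient would commit a major deviation. That is only a possibility. Such a site has normally not judged the criterion met, the example is generic, and a committee confirms each major deviation.

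Nor does all follow-up end. The Early Discontinuation visit includes a full echocardiogram, KCCQ, NYHA class, ECG and laboratory tests. Protocol 8.1.5 asks for an end-of-study visit four weeks after the last dose if possible, and 8.4.1.7 has SAEs reported for at least four weeks after it. For pVO2, placebo-based imputation and a tipping-point analysis are planned in any case (SAP 7.7.2). The NYHA and SRT rules apply to dropout for any reason, and many patients with worrying ECG findings could not safely do a maximal CPET under any wording. All of this stands and limits the size of the point.

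**Conclusion.** The point holds as a wording inconsistency with a probably very small effect. Section 8.3.4 goes directly to trial withdrawal where Section 7 would stop IP and keep follow-up where safe and feasible, and a literal reading could needlessly lose data.

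On the assumptions above, three aficamten patients all able to exercise shift the difference by at most about 0.033 mL/kg/min; with half able, by at most 0.017. The direction depends on the imputation in force. The counts and off-drug effects are assumed, since the documents give no ECG withdrawal rate. A reader might infer that the primary result or the power is at risk. The documents do not support that: the stated power reproduces, and the sample size already allows for 10% missing.

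**What to change.** Change both the trigger and the action in Protocol 8.3.4. Changing the action alone would order follow-up to continue for a patient just judged better off out of the trial. Suggested text:

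> If, in the investigator's or designee's medical judgment, ECG findings make continued IP or a trial procedure (eg, CPET) not in the patient's best interest, IP will be interrupted or permanently discontinued under Sections 7.1 and 7.2 and/or that procedure omitted, and the patient will be followed under Sections 7.2.1 and 7.3 whenever safe and feasible.

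This keeps interruption as the first step and leaves the investigator free to limit follow-up to phone or records.

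The cost is one sentence in a protocol amendment, which needs IRB/IEC approval (10.1.1), so it is best bundled with another amendment. Amendment 04 is dated 08 December 2023 and the SAP gives the studied period as 2022 to 2023, so few patients may benefit. If none remain on study, the sponsor can still make sure that sites which kept following such patients are not recorded as deviating, and carry the wording into later protocols. Observed off-drug values may slightly lower the estimated effect, as the primary estimand intends.
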